8.3. Missing Data

The data after the receipt of rescue therapy will be handled before imputation as below:

Use of rescue therapy: Except OC, all efficacy data on or after the receipt of rescue therapy will be considered as 'not evaluable data' for analysis. For analysis purpose it will be replaced by the worst possible score for endpoint and considered as 'treatment failure'. However, in OC analysis, all observed data even after the receipt of rescue treatment will be included for analysis, i.e., no imputation for missing data.

In case of diary data, if the date of rescue therapy use is within the analysis visit window, the subject at the analysis visit will be treated as treatment failure except for OC analysis, and the weekly average will be imputed using the worst-case value.

Further details for the data handling for rescue therapy are in section 7.

The primary method to impute the missing values will be as follows:

Continuous Endpoints: For continuous endpoints during Initial Period, the MI under MAR assumption approach and the MMRM approach will be used to handle the missing data for the selected secondary endpoints.

QoL endpoints (e.g., DLQI/cDLQI, EQ-5D, PIQ) may be imputed using last observation carried forward (LOCF), where applicable.

Binary Endpoints: All missing values will be treated as a non-responder for the binary endpoints for primary, key secondary and secondary endpoints during Initial Period. To assess the robustness of non-responder analysis for primary and key secondary endpoints, a tipping point analysis will be performed. The MI under MAR assumption, LOCF, and OC will be used as sensitivity analysis to impute the missing values for the primary and key secondary endpoints.

Adverse events and concomitant medications/procedures: Missing assessment times will have imputed times for the purposes of assessing treatment emergence for AEs or classifying medications/procedures into prior/concomitant. However, the assessment times (start date, stop date, and time if collected from CRF) without imputation will be presented in the listings.

For the start of a concomitant medication/procedure or AE:

- Only the year is reported: If the subject received the first study drug dose in the year reported, then the date of the first dose of study drug will be used as the start date; otherwise, January 1 of the year reported will be used as the start date.
- The month and year are reported: If the subject received the first study drug in the month and year reported, then the date of the first dose of study drug will be used as the start date; otherwise, the first day of the month and year will be used as the start date.

This document is confidential.

- The time is collected but missing: If the start date is the same as the date the subject started receiving study drug, then the time of the first dose of study drug will be used as the start time; otherwise, 00:00 will be used as the start time.

For the end of a concomitant medication/procedure or AE:

- Only the year is reported: The earlier between December 31 of the year reported and the date of the last study contact with the subject will be used as the stop date.
- The month and year are reported: The earlier between the last date of the month and year reported and the date of the final contact with the subject will be used as the stop date.
- The time is collected but missing: 23:59 (or 23:59:59 if collected up to seconds) will be used as the stop time.

If an AE has the start date completely missing and the stop date on/after the first dose date of study drug, this AE will be considered as treatment emergent (TEAE).

If a medication/procedure has the stop date completely missing, this medication/procedure will be considered as ongoing and concomitant. If the start date of a medication/procedure is completely missing and impossible to identify different by stop date, this medication will be considered as concomitant.

8.4. Analysis Visit Windows

Efficacy by-visit summaries will use the analysis visit. Unscheduled and early termination visits will be windowed based on the following analysis visit window which is based on study day. If multiple measurements are taken within the same window, the one taken closest to the target study day will be used for the analysis. If there are multiple measurements with same difference from target day, the later assessment should be used for the analysis.

Table 8-1: Analysis Visit Window

Analysis Visit	Target Study Day	Visit Window for EASI, IGA, BSA, SCORAD, Rescue therapy	Visit Window for PGIS-P, PGIS-SD, PGIC-P, PGIC-SD	Visit Window for DLQI/cDLQI, HADS, EQ-5D, POEM, WPAI:AD, Pain intensity/frequency, PGAD, PGAT, PIQs*
Baseline	1	<=1	<=1	<=1
Week 4	29	2 to 42	NA	NA
Week 8	57	43 to 70	2 to 81	2 to 84
Week 12	85	71 to 98	NA	NA
Week 15	106	NA	82 to 108	NA
Week 16	113	99 to 126	>=109	85 to 168 except for PIQs; >=85 for PIQs
Week 20	141	127 to 154	NA	NA
Week 24	169	155 to 182	NA	NA
Week 28	197	183 to 210	NA	NA
Week 32	225	211 to 238	NA	169 to 280 except for PIQs
Week 36	253	239 to 266	NA	NA
Week 40	281	267 to 294	NA	NA
Week 44	309	295 to 322	NA	NA

This document is confidential.

Statistical Analysis Plan for Interventional Studies

Sponsor: Galderma Research & Development, LLC; Protocol No.: RD.06.SPR.118161

Week 48	337	>=323	NA	>=281 except for PIQs
---------	-----	-------	----	-----------------------

* PIQs assessment is available during Initial period only. Visit window after Week 16 will not be applicable for PIQs.

Analysis visit of diary (ePRO) data will be defined depending on the data collection as below.

For the diary data at post-baseline visit, only the diary data assessed within the timeframe below (+1 hour to end time in spec) will be considered for analysis. If >1 diary recorded on a day (within window), only one of them to take for analysis (i.e. latest one for evening diary, earliest one for morning diary).

- Evening assessment (PP/AP NRS, Topical medication, PCS) recorded from 17:00:00 to 00:59:59
- Morning assessment (SD NRS, morning sleep diary) recorded from 5:00:00 to 17:59:59

Consecutive daily assessment:

For the evening assessments (PP NRS, AP NRS) during Initial Period, the daily data collected up to Week 16 will be classified into analysis visits considering the data during the 7 days immediately preceding the target study day of analysis visit. Similarly, for the morning assessment (SD NRS, morning sleep diary) during Initial Period, the 7 days data up to the target study day will be classified into analysis visit. Details of the analysis visit window are in the table below. Only the data belongs to Initial Period will be considered for classifying the analysis visit in Initial Period.

Table 8-2: Analysis Visit Window for Evening and Morning Assessments during Initial Period

Analysis Visit	Target Study Day of Analysis Visit	Visit Window for evening assessment (PP NRS, AP NRS, Topical Medication)	Visit Window for morning assessment (SD NRS, morning sleep diary)
Baseline*	1	-7 to -1	-6 to 1
Week 1	8	1 to 7	2 to 8
Week 2	15	8 to 14	9 to 15
Week 3	22	15 to 21	16 to 22
Week 4	29	22 to 28	23 to 29
Week 5	36	29 to 35	30 to 36
Week 6	43	36 to 42	37 to 43
Week 7	50	43 to 49	44 to 50
Week 8	57	50 to 56	51 to 57
Week 9	64	57 to 63	58 to 64
Week 10	71	64 to 70	65 to 71
Week 11	78	71 to 77	72 to 78
Week 12	85	78 to 84	79 to 85
Week 13	92	85 to 91	86 to 92
Week 14	99	92 to 98	93 to 99
Week 15	106	99 to 105	100 to 106
Week 16**	113	106 to 112 before dosing	107 to 113

* if there are less than 4 days non-missing data available within window, the lower bound of interval will be extended up to 7 additional days to obtain 4 days non-missing data for Baseline weekly score calculation. The timeframe window will not be considered.

** if <4 days non-missing data within Week 16 window, the upper bound will be extended first up to +5 days to obtain 4 non-missing data. If still <4 non-missing data after extending the upper bound, the lower bound will be extended again up to +5 days to obtain 4 days non-missing data. For evening assessment, only the data before Week 16 dosing (or re-randomization if missing Week 16 dosing) will be considered for Initial Treatment Period analysis.

This document is confidential.

In case topical medication used (daily evening assessment throughout the study), 7 days immediately preceding the target study day will be considered to define analysis visit during the study. The same window with evening assessment (PP NRS, AP NRS) in Table 8-2 will be used for Initial Period. For Maintenance Period, the target study day of Week 20, Week 24, Week 28, Week 32, Week 36, Week 40, Week 44 and Week 48 will be Day 141, Day 169, Day 197, Day 225, Day 253, Day 281, Day 309, and Day 337. If the data reported within analysis visit window but after week 16 dosing, it won't be part of initial period. The extended timeframe (+1 hour to end time) to be considered.

Intermittent daily assessment before the visit:

For the evening assessments (PP NRS and AP NRS during Maintenance Period, and PCS assessment), the 7 days immediately preceding the actual subject visit date will be classified into the analysis visit. i.e., from 'actual subject visit date – 7 days' to 'actual subject visit date – 1 day'. Similarly, for the morning assessments (SD NRS, morning sleep diary), the 7 days data from 'actual subject visit date – 6 days' to 'actual subject visit date' will be classified into the analysis visit. In maintenance period, the diary data will not be collected daily, so consider dosing date/time and include data for calculation only if it's done within analysis visit window/timeframe and before dosing.

In case of missing/skipped visit, unscheduled or early termination visit, the diary data will be windowed based on the study day (see Tables 8-3 and 8-4). If a subject missed/skipped a visit due to any reason (e.g., skipped a visit due to COVID-19), the diary data which have been reported during that time will be mapped to the analysis visit based on the study day and 7 days consecutive data will be classified into the analysis visit as in the tables below. For the unscheduled or early termination visit data, the same approach will be applied to window the data into analysis visit.

In case of evening diary (e.g., PP/AP NRS), the data within analysis visit window but after dosing on the clinic visit date will not be used for weekly score calculation at the corresponding analysis visit.

Table 8-3: Analysis Visit Window for Missing/Skipped Visit, Unscheduled or Early termination Visit for PP/AP/SD NRS and Sleep Diary

Analysis Visit	Target Study Day of Analysis Visit	Visit Window for evening assessment (PP NRS, AP NRS)*	Visit Window for morning assessment (SD NRS, morning sleep diary)
Week 24	169	162 to 168	163 to 169
Week 32	225	218 to 224	219 to 225
Week 40	281	274 to 280	275 to 281
Week 48	337	330 to 336	331 to 337

* for evening diary, only the data before dosing on the clinic visit date will be considered for analysis.

Table 8-4: Analysis Visit Window for Missing/Skipped Visit, Unscheduled or Early Termination Visit for PCS Assessments

Analysis Visit	Target Study Day of Analysis Visit	Visit Window for PCS
Baseline	1	-7 to -1
Week 8	57	50 to 56
Week 15	106	99 to 105
Week 16*	113	106 to 112 before dosing

This document is confidential.

* if <4 days non-missing data within Week 16 window, the upper bound will be extended first up to +5 days to obtain 4 non-missing data. If still <4 non-missing data after extending the upper bound, the lower bound will be extended again up to +5 days to obtain 4 days non-missing data. Only the data before Week 16 dosing (or re-randomization if missing Week 16 dosing) will be considered for Initial Treatment Period analysis.

For efficacy, where two or more assessments (including both scheduled and unscheduled assessments) are available for the same visit interval, the one closest to the target visit date will be used for the summary and analyses. Safety and pharmacokinetics data will not be windowed for by-visit summary. i.e., scheduled visit data will be used for analysis.

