- ^c Subjects will complete PCS, PGIS-P, PGIC-P, PGIS-SD, and PGIC-SD assessments at Week 15 (prior to the Week 16 visit) for test-retest validation of itch and sleep PRO measures. For PGIS-P and PGIC-P, subjects will complete a single assessment 8 days prior to the Week 16 visit. For PGIS-SD and PGIC-SD, subjects will complete a single assessment 7 days prior to the Week 16 visit. For PCS, subjects will complete the assessment for 14 consecutive days before the Week 16 visit.
- SAP Version: Final Version 1.0, 09-Nov-2022
- Controlled Document ID: 3903A.01, Effective Date 31-Aug-2020
- Filing requirements: TMF

CONFIDENTIAL

Statistical Analysis Plan for Interventional Studies

Sponsor: Galderma Research & Development, LLC; Protocol No.: RD.06.SPR.118161

^d Subjects discontinued prematurely should complete ET assessments according to: Visit 6/Week 16 if during the initial treatment period **or** Visit 14/Week 48 if during the maintenance period **and** a final/follow-up visit 12 weeks after the last study drug injection (for subjects not participating in the LTE study). Subjects who require rescue therapy (with or without study medication discontinuation) must continue with study visits until: Visit 6/Week 16 if during the initial treatment period **or** until Visit 10/Week 32 if during the maintenance period to be considered for LTE eligibility. (If during the maintenance period, rescue is needed after the Week 32 visit, no wait period is required.)

^e The follow-up visit will be conducted for subjects who decline or are not eligible to enter the LTE study and should be conducted 12 weeks after the last study drug injection. (The follow-up visit is not required for subjects who will rollover to the LTE study.)

^f The run-in period begins at least 2 weeks (i.e., 14 days) before Day 1/baseline. Subjects receiving rescue therapies during the run-in period are not eligible to participate in the study.

^g Patient-reported outcome assessments and designated safety measurements should occur before investigator assessments, laboratory sample collections, and study drug administration.

^h P/Qs will be implemented in all countries where a validated questionnaire in the local language is available.

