ⁱ SD NRS and morning sleep diary questions to be recorded by subjects once daily in the morning and if possible, within 1 hour of getting out of bed (Visit 1/Screening through Visit 6/Week 16). PP NRS, AP NRS, and evening sleep diary questions to be recorded by subjects once daily in the evening (Visit 1/Screening through Visit 6/Week 16), beginning after the screening visit. Topical background therapy use (not including moisturizer) to be recorded by subjects once daily in the evening throughout the study, beginning after the screening visit. On designated visits, PGIS-SD and PGIC-SD should be recorded after the SD NRS and sleep diary in the morning before investigator assessments, laboratory sample collection, and study drug administration; PGIS-P and PGIC-P should be recorded after the PP NRS and AP NRS in the evening the day prior to designated visits.

^j Pruritus assessments (i.e., PP NRS, AP NRS, PCS, PGIS-P, PGIC-P) will be recorded the evening before the clinic visit. If a subject does not complete the PCS, PGIS-P, and PGIC-P in the evening before a scheduled visit, the subject will be allowed to complete the assessment the following day at the clinic visit before investigator assessments, laboratory sample collection, and study drug administration.

^k Assessments to be completed by subjects for 7 consecutive days before the designated target visit dates during study treatment.

^l Optional subject interviews will be conducted at the end of the initial treatment period between Week 16 and Week 18.

^m Optional photographs of AD lesions will be performed only for consenting subjects at selected sites.

ⁿ Subjects with a history of asthma will complete the ACT (and PEF testing) at each scheduled visit. Subjects with de novo asthma will complete the ACT (and PEF testing) beginning from de novo diagnosis and at all subsequent scheduled visits.

^o At screening, the investigator should specifically question all subjects about any medical history of asthma and their respiratory health (eg, wheezing, coughing, allergies, infections). A respiratory examination will be required for all subjects at all scheduled visits.

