8.2. Key Definitions

Screening Period is a Period of approximately 2-4 weeks before Day 1/Baseline during which subject eligibility is evaluated and standardized background topical therapy is introduced over a run-in Period of at least 2 weeks before Day 1/Baseline.

The Initial Period is defined as Day 1/Baseline to Week 16 (before the Week 16 dose, with last dose at Week 12). If early discontinued during treatment period, it is defined as the period until 4 weeks after last dosing date or early termination date whichever is earlier.

The Maintenance Period is defined as Week 16 (Maintenance Baseline) to Week 48. If early discontinued during treatment period, it is defined as the period until 4 weeks after last dosing date or early termination date whichever is earlier.

Follow-up Period is defined as the post end of treatment period (i.e., 1 day after end of treatment period) to Follow-up visit in respective treatment period.

The Baseline value of the Initial Period will be taken as latest valid value prior to first injection of study drug. For subjects randomized but not treated, the Baseline value will be the latest value prior to the randomization. Week 16 measurements will serve as Baseline measurements for the Maintenance Period (i.e., Maintenance Baseline). If Week 16 measurements are missing for re-randomized subjects, the last valid non-missing measurement in the Initial Period (i.e., before the dosing for Maintenance Period at Week 16 visit) will be taken as the Baseline measurement for the Maintenance Period.

For diary data (e.g., Peak Pruritus (PP) NRS, Sleep disturbance (SD) NRS), the Baseline values will be the weekly prorated average of non-missing subject diary scores reported during the 7 days. A minimum of 4 daily scores out of the 7 days is required to calculate the weekly prorated average score. Refer the details for the analysis visit window for diary data in Section 8.4.

The date of first treatment is defined as the date of first injection of study drug. The date of first treatment is the Baseline date.

The date of last treatment is defined as the date of last injection of study drug.

Study day is defined as the number of days from the date of first treatment and will be calculated as follows:

This document is confidential.

- If the event date \geq date of first treatment, study day = event date – date of first treatment + 1. Study Day 1 is therefore defined as the day of first treatment.

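### The fixed Day 108/109 cut between Week 15 and Week 16 for PGIS and PGIC falls among readings that an allowed Week 16 visit produces, so a completed Week 16 reading can be filed elsewhere

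*SAP*

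**What the plan says.** Collection is tied to the Week 16 visit. In the notes to SAP Table 4-3, the Week 15 retest of the itch items is set as follows: "For PGIS-P and PGIC-P, subjects will complete a single assessment 8 days prior to the Week 16 visit". For the sleep items: "For PGIS-SD and PGIC-SD, subjects will complete a single assessment 7 days prior to the Week 16 visit". For the Week 16 reading itself, "PGIS-P and PGIC-P should be recorded after the PP NRS and AP NRS in the evening the day prior to designated visits", while "PGIS-SD and PGIC-SD should be recorded after the SD NRS and sleep diary in the morning before investigator assessments". If the itch items are missed that evening, they may be completed at the clinic the next day. The same table allows the Week 16 visit 5 days either side of target and shows Week 15 as a no-visit column with a window of ±0.

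Analysis is tied to study day. SAP 8.2 sets the origin: "Study Day 1 is therefore defined as the day of first treatment". In Table 8-1, Week 15 for these four items has target Day 106 and window 82 to 108. Week 16 has target Day 113 and takes everything from Day 109 on. SAP 8.4 then gives the selection rule, "If multiple measurements are taken within the same window, the one taken closest to the target study day will be used for the analysis", and the tie rule, "If there are multiple measurements with same difference from target day, the later assessment should be used for the analysis".

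On scope, SAP 8.4 opens by saying that efficacy by-visit summaries use the analysis visit, and continues: "Unscheduled and early termination visits will be windowed based on the following analysis visit window which is based on study day". Its closing paragraph applies the closest-to-target rule for efficacy to scheduled and unscheduled assessments alike, and exempts only safety and pharmacokinetic data from windowing.

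**The concern.** The readings move with the visit and the cut does not. When the visit is early, a Week 16 reading taken exactly as instructed can land on Day 108 or before and be filed as Week 15. When the visit is late, the retest can land on Day 109 or after, where it competes with the real Week 16 reading and may win on distance to Day 113. In both cases the subject and the site have complied.

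At stake are the Week 16 columns of Tables 14.2.3.19.1.2 (PGIS-P and PGIS-SD) and 14.2.3.19.1.3 (PGIC-P and PGIC-SD). These are observed-case summaries, so a misfiled reading is not imputed: it drops out of Week 16 or is replaced by one taken a week earlier.

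**Working it through.** **Plan's own figures.** Target day = 7 × week + 1. Week 15: 7 × 15 + 1 = 106. Week 16: 7 × 16 + 1 = 113. Both agree with Table 8-1. The allowed Week 16 visit is Day 113 ± 5, that is Days 108 to 118, or 11 possible days.

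**Reading days for a visit on Day v.** Itch: retest v − 8, Week 16 reading v − 1 (or v if completed at the clinic). Sleep: retest v − 7, Week 16 reading v.

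**Case A: the retest follows the actual visit.** Apply the windows, then closest to target, then later if tied. Cells marked *filed* show what goes to Week 15 / Week 16.

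| Visit day | Itch: retest, reading | Itch: filed | Sleep: retest, reading | Sleep: filed |
|---|---|---|---|---|
| 108 | 100, 107 | reading / empty | 101, 108 | reading / empty |
| 109 | 101, 108 | reading / empty | 102, 109 | correct |
| 110–115 | 102–107, 109–114 | correct | 103–108, 110–115 | correct |
| 116 | 108, 115 | correct | 109, 116 | empty / correct |
| 117 | 109, 116 | empty / correct | 110, 117 | empty / retest |
| 118 | 110, 117 | empty / retest | 111, 118 | empty / retest |

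Two rows in full:
- Itch, visit Day 108: both readings fall in 82 to 108. Distances to Day 106 are |100 − 106| = 6 and |107 − 106| = 1, so the Week 16 reading becomes Week 15 and Week 16 is empty.
- Itch, visit Day 118: both fall at 109 or later. Distances to Day 113 are |110 − 113| = 3 and |117 − 113| = 4, so the retest becomes Week 16.

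Week 16 is empty or wrong on 3 of 11 days for itch (108, 109, 118) and 3 of 11 for sleep (108, 117, 118). Week 15 is empty or wrong on 4 of 11 for each. If the itch items are completed at the clinic, Day 109 is rescued and Week 16 fails on Days 108 and 118 only; at Day 117 the retest (Day 109) and the reading (Day 117) are both 4 days from target and the tie rule keeps the reading.

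**Case B: the retest stays at its planned date** (Day 105 for itch, Day 106 for sleep). Week 16 is empty at visit Days 108 and 109 for itch (2 of 11) and at Day 108 for sleep (1 of 11). With itch items completed at the clinic it is Day 108 only (1 of 11). The retest is never reported as Week 16. Week 15 is wrong on 1 of 11 days for itch (visit Day 108, where Days 105 and 107 tie around 106 and the later is taken) and on none for sleep.

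**Would moving the cut help?** Not in Case A. Retests span Days 100 to 110 (itch) and 101 to 111 (sleep), and Week 16 readings span 107 to 117 and 108 to 118, so the ranges overlap. For every first Week 16 day from 105 to 113, at least 4 of the 11 visit days still put a reading in the wrong window.

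**The case against.** The strongest reply is scope. The sentence that introduces Table 8-1 names only unscheduled and early termination visits. If scheduled readings keep their nominal visit label, nothing goes wrong. A reader might infer that the SAP as written certainly misfiles on-schedule readings; that is too strong, because the text is ambiguous. The reply does not dispose of the point either. No rule says scheduled readings keep their label, and the end of SAP 8.4 brings scheduled assessments under the closest-to-target rule. Two programmers could reasonably produce different Week 16 columns.

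Second, the retest may not move with the visit. The note to Table 4-3 does not say whether its 7 or 8 days count back from the actual or the planned date, the Week 15 column has a window of ±0, and a prompt due a week ahead has to be set from a planned date. This stands. It removes every case of the retest being reported as Week 16 and reduces the counts to Case B, but the empty Week 16 after an early visit remains.

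Third, most instrument subsections of SAP 10.3 are blacked out, so a PGIS/PGIC rule could exist there. That cannot be excluded; if it does, SAP 8.4 should be made to agree with it.

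Fourth, a reader might describe the windows as narrower than the ±5-day visit allowance. They are not: Week 15 spans 108 − 82 + 1 = 27 days and Week 16 has no upper limit. The fault is where the cut sits.

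**Conclusion.** The point holds as a windowing defect of small practical size. It assumes that scheduled PGIS and PGIC readings are windowed by Table 8-1. On that assumption, Week 16 is empty for a visit on Day 108 (both measures) or Day 109 (itch recorded the evening before), wherever the retest falls. Reporting the retest as Week 16, and the count of 3 of 11 visit days per measure, need the further assumption that the retest follows the actual visit. Otherwise the count is 2 of 11 for itch and 1 of 11 for sleep.

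Two larger conclusions are tempting and not supported. One is that 3/11, or 27%, of Week 16 values would be affected. That requires visits spread evenly over the window, for which the documents give no evidence; every Week 16 error sits at a shift of 4 or 5 days, so the real share is probably small. The other is that efficacy conclusions or the test-retest validation are compromised. Only the two descriptive tables are touched. The co-primary and key secondary endpoints do not use this column of Table 8-1, the psychometric analysis has its own plan (protocol 10.1.8), and PGIS and PGIC data are also presented in Listing 16.2.6.15.

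**What to change.** In SAP 8.4, state that for scheduled visits PGIS and PGIC are assigned relative to the actual Week 16 visit date: Week 16 is the reading from the evening before or the day of the visit, and Week 15 is the scheduled retest 7 to 8 days before. Keep the fixed windows of Table 8-1 for missed, unscheduled and early termination visits only. SAP 8.4 already takes this approach for the Pruritus Categorical Scale, with Table 8-4 as the fallback. In Case A this gives 0 of 11 visit days wrong.

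The text should also say whether the handheld device sets the retest from the planned or the actual visit. If from the planned date, the interval to the actual visit for the itch items runs from 108 − 105 = 3 to 118 − 105 = 13 days, so Week 15 should be defined as the scheduled retest rather than by an exact 7- or 8-day offset.

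The cost is one extra derivation rule and its programming. No new data are needed.
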